5.7.6. Other analysis

In patients receiving a booster in Group 4, the number of days between the booster and first vaccination will be descriptively summarized.

5.8. Planned Analyses

Unplanned interim analyses may be performed if requested by health authorities.

5.8.1. Independent Data Monitoring Committee (IDMC)

An IDMC is established to monitor data on an ongoing basis to ensure the continuing safety of the participants enrolled in this study. The IDMC reviews safety and reactogenicity data as indicated below.

Prior to this amended SAP version, the IDMC met and reviewed:

- all available safety and reactogenicity data in the Sentinel (n=5) Cohort once they had received the first dose of Ad26.COV2.S at $5x10^{10}$ vp and completed the Day 8 visit
- all available safety and reactogenicity data once the 22 participants in the Sentinel (n=5) and Safety Cohort (n=17) once they had received the first dose of Ad26.COV2.S at 5x10¹⁰ vp and completed the Day 8 visit

The data review included the following: participant disposition; demographics and baseline characteristics; unsolicited AEs, SAEs, AESI, and solicited AEs (local and systemic). The summaries of these data were prepared according to the corresponding sections in this SAP and as further outlined in the DPS.

Based on their review, the IDMC confirmed that the safety profile of 1 dose of Ad26.COV2.S at 5×10^{10} vp was considered acceptable and no safety concerns were identified. The remaining participants (who have received their last COVID-19 vaccination at least 4 months prior to receiving the study vaccine or are vaccine naïve participants) could be enrolled to receive 1 dose of Ad26.COV2.S at 5×10^{10} vp.

The IDMC also conducts routine safety reviews of data based on descriptive safety tables and listings from all accumulated safety data at that point in time using similar summaries as prepared for the Sentinel and Safety Cohort. After each review, the IDMC makes recommendations regarding the continuation of the study.

The IDMC responsibilities, authorities, and procedures are provided in its charter. For more details see CTP Section 9.6.

5.8.2. Primary Analysis

The primary analysis of safety and immunogenicity will be performed when all adult participants have completed the visit that takes place approximately 42 days postpartum in all groups or if adult participants are discontinued earlier. The analysis will include safety (e.g. AEs, SAEs, and pregnancy outcomes) and available immunogenicity data (e.g. S-ELISA and MSD) for all adult participants and neonates/infants and in cord blood at the time of delivery. The primary analysis will include all data up to and including the Day 42 postpartum follow-up visit. The results of this analysis may be used for regulatory submissions.

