1.1. Objectives and Endpoints

Objectives	Endpoints
Primary	
To assess the safety and reactogenicity of Ad26.COV2.S administered intramuscularly	• Solicited local and systemic AEs for 7 days after vaccination, or until resolution.
(IM) as a 1-dose (5×10 ¹⁰ vp) schedule in adult participants, during the 2 nd and/or 3 rd trimester of pregnancy, and (potentially) postpartum.	• Unsolicited AEs for 28 days after vaccination.
	• Serious adverse events (SAEs) and Adverse Events of Special Interest (AESI) throughout the study (from vaccination until end of the study, i.e., at least 12 months after delivery).
	• Medically-attended adverse events (MAAEs) until 6 months after vaccination
	• AEs leading to study discontinuation (during the entire study).
To assess the humoral immune response in peripheral blood of adult participants to Ad26.COV2.S administered IM as a 1-dose $(5 \times 10^{10} \text{ vp})$ schedule, during the 2 nd and/or 3 rd trimester of pregnancy, 28 days after vaccination.	• Serological response to vaccination as measured by enzyme-linked immunosorbent assay (ELISA; [S-ELISA, EU/mL]), 28 days after vaccination.
Secondary	
Adults	
To assess safety of the booster dose of Ad26.COV2.S at 5×10^{10} vp on participants	• Solicited local and systemic AEs for 7 days after booster vaccination, or until resolution.
who were vaccine naïve at study entry.	• Unsolicited AEs for 28 days after vaccination.
	• SAEs and AESI throughout the study (from vaccination until end of the study, i.e., at least 12 months after delivery).

Objectives	Endpoints
	MAAEs until 6 months after vaccination
	• AEs leading to study discontinuation (during the entire study).
To assess pregnancy outcomes in adult participants who have received Ad26.COV2.S during the 2 nd and/or 3 rd trimester of pregnancy.	• Pregnancy outcomes (including, live term birth, live preterm birth, stillbirth, and abortion) (non-exhaustive).
To assess pregnancy-related AEs in adult participants who have received Ad26.COV2.S during the 2 nd and/or 3 rd trimester of pregnancy.	• Pregnancy-related AEs throughout pregnancy (including gestational diabetes, gestational hypertension, premature rupture of membranes, premature labor, premature uterine contractions, poor or restricted fetal growth, pre-eclampsia, eclampsia, vaginal or intrauterine hemorrhage) (non-exhaustive).

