1.2. Study Design

This is an open-label multicenter, Phase 2 study in healthy pregnant (2nd and/or 3rd trimester of pregnancy) participants ≥ 18 to ≤ 45 years of age to evaluate safety, reactogenicity, immunogenicity, and pregnancy outcomes. In this study, Ad26.COV2.S will be assessed as a single dose of 5×10^{10} vp in pregnant women who were previously vaccinated with another COVID-19 vaccine regimen or who were vaccine naïve at study entry.

A target of 240 adult participants in the 2nd or 3rd trimester of pregnancy (Week 16 to Week 38 of gestation, inclusive) was to be enrolled. Efforts were made to ensure good representation in terms of race and ethnicity. Enrollment was staggered and started with recruitment of vaccine naïve Sentinel participants (n=5) followed by an additional larger Safety Cohort (n=17) who all received 1 dose of Ad26.COV2.S vaccine at 5×10^{10} vp. Based on the safety data of those subjects, the IDMC confirmed that the safety profile of 1 dose of Ad26.COV2.S at 5×10^{10} vp was considered acceptable and no safety concerns were identified. The remaining participants (who have received their last COVID-19 vaccination at least 4 months prior to receiving the study vaccine or are vaccine naïve participants) were to be enrolled to receive 1 dose of Ad26.COV2.S at 5×10^{10} vp. They will preferably be equally distributed between the following groups, per their COVID-19 vaccination histories:

- **Group 1**: Previous primary vaccination (2-doses) or homologous booster vaccination with Comirnaty (Pfizer-BioNTech) or SpikeVax (Moderna)
- **Group 2**: Previous primary vaccination (1-dose) or homologous booster vaccination with Ad26.COV2.S (Janssen)
- **Group 3**: Previous COVID-19 vaccination, irrespective of previous schedule and vaccine (includes heterologous regimens) and excluding schedules for Groups 1 and 2
- Group 4: Vaccine naïve participants, including those who are in Sentinel and Safety Cohorts

Prior to CTP amendment 4, the sample size of each of the groups was preferably equally distributed but flexible with a target to recruit at least 40 participants in Groups 1 to 3 and at least 25 participants in Group 4. Participants were stratified by pregnancy stage at the time of enrollment (Weeks ≥ 16 to < 28 or Weeks ≥ 28 to ≤ 38), with a goal of at least approximately 25% participants per trimester, per group.

As of CTP amendment 7, participant enrolment in this study was ceased.

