5.3. Primary Endpoint(s) Analysis

5.3.1. Definition of Endpoints

Safety and reactogenicity of Ad26.COV2.S (first vaccination) in adult participants

- Solicited local and systemic AEs for 7 days after (first) vaccination, or until resolution
- Unsolicited AEs for 28 days after (first) vaccination
- SAEs and AESI throughout the study (from first vaccination until end of the study, i.e. at least 12 months after delivery)
- MAAEs until 6 months after the last vaccination
- AEs leading to study discontinuation (during the entire study)

Refer to Sections 5.6.1 for more details on adverse events definitions.

Humoral Immune Response in peripheral blood of adult participants

• Serological response to vaccination as measured by enzyme-linked immunosorbent assay (ELISA; [S-ELISA, EU/mL]), 28 days after vaccination

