5.3.3. Analysis Methods

Safety and reactogenicity of Ad26.COV2.S in adult participants

The primary safety and reactogenicity objectives for adult participants of the study will be evaluated with AEs, SAEs, AESIs and MAAEs as detailed in Section 5.6.1 for definitions and analyses methods of adverse events.

Refer to Section 5.7.1 for definitions and analyses methods of immunogenicity endpoints.

Analyses will also be performed by subgroup: gestational age group, participant age group at baseline, and the SARS-CoV-2 serostatus at baseline. Refer to Section 5.7.5 for subgroup definitions.

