5.6.1.3. Analysis of Adverse Events

Solicited AEs (shown in output) are extracted from the investigator assessment pages of the CRF and will be recorded in the Clinical Event SDTM domain. Only Solicited AEs with onset within 7 days after vaccination (post-dose 1, post-booster [booster in Group 4], and post-dose 1+ post-booster) will be reported in tables. For unsolicited AEs, only the AEs within the 28-day period following (primary or booster) vaccination will be presented in the safety tables except for SAEs, AEs leading to treatment/study discontinuation (incl. MAAE leading to treatment/study discontinuation) and AESIs which will be captured and tabulated in the outputs covering the whole study period (i.e. up to 12 months postpartum), and MAAEs which will be captured and tabulated for all participants from the first vaccination until 6 months after (each) vaccination.

Number and percentage of participants with at least one particular AE (unsolicited/solicited) will be tabulated. Unsolicited AEs will be summarized by System Organ Class and Preferred Term. Solicited AEs will be summarized by class (administration site/systemic) and Preferred Term.

For solicited AEs following tables will be provided: summary, by worst severity grade, at least grade 3, related (systemic only), time to onset (in days) and duration (in days) for most frequent events (>5%) and body temperature. Note: Duration is defined as number of days from the start of the event until resolution of the event. The time to first onset is defined as (date of first onset – reference date + 1). The reference date is the start date of the vaccination period.

For unsolicited AEs, the following tables will be provided: summary table (including SAE, AESI, MAAEs, AEs leading to treatment/study discontinuation, fatal outcome, and discontinuation), all events, most frequent (>5%), at least grade 3, related, and SAEs. The proportion of AEs resulting in a medically attended visit (other than routine health maintenance visits) will also be tabulated.

Pregnancy-related AEs in adult participants (including gestational diabetes, gestational hypertension, premature rupture of membranes, premature labor, premature uterine contractions, poor or restricted fetal growth, pre-eclampsia, eclampsia, vaginal or intrauterine hemorrhage [non-exhaustive]) will be tabulated separately. The complete list of preferred terms to be included as pregnancy related AEs is provided in Section 6.8.

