5.6.1.5. Missing Data

Missing data will not be imputed. Participants who do not report an event will be considered as participants without an event. An AE with a missing severity or relationship will be considered as an AE reported, but will be considered as not reported for the severity or relationship. For example, an AE with missing severity will be considered as an AE reported for the analysis of any grade but will be considered as not reported for the analysis of at least grade 3.

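### The primary analysis stops at the 42-day postpartum visit, before the 6-month MAAE window closes for most women if the cut is per woman, and follow-up then differs about two-fold between the gestational-age subgroups

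*SAP*

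**What the plan says.** SAP 1.1 lists this endpoint under the primary safety objective: "Medically-attended adverse events (MAAEs) until 6 months after vaccination". SAP 5.3.1 words it as "MAAEs until 6 months after the last vaccination". SAP 5.6.1.3 describes "MAAEs which will be captured and tabulated for all participants from the first vaccination until 6 months after (each) vaccination" and makes no exception for the primary analysis. For a boosted Group 4 participant, the last two wordings carry the window further still.

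The primary analysis in SAP 5.8.2 is triggered when all adults have "completed the visit that takes place approximately 42 days postpartum in all groups" or have discontinued earlier. On content it adds: "The primary analysis will include all data up to and including the Day 42 postpartum follow-up visit". The same section says the results may be used for regulatory submissions. Table 4 (5.1.2.1) defines a matching safety interval, from first vaccination to Postpartum Day 43.

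Three other provisions matter:

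- Enrolment covers "Week 16 to Week 38 of gestation, inclusive" (1.2).
- On missing data, 5.6.1.5 says: "Participants who do not report an event will be considered as participants without an event". Section 5.1 takes percentages over the participants in the population and phase. No person-time or censoring method is given.
- For the primary endpoints, 5.3.3 says: "Analyses will also be performed by subgroup: gestational age group, participant age group at baseline, and the SARS-CoV-2 serostatus at baseline".

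The final analysis (5.8.3) follows when all adults and infants have completed their final visits. Nothing in the SAP defers the 6-month MAAE endpoint to that point or labels it incomplete before then.

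**The concern.** How long a woman has been observed after vaccination at the primary analysis depends on how late in pregnancy she was vaccinated. A woman vaccinated early may have her whole 6-month window behind her, while one vaccinated near term has about two months. A crude percentage treats them alike, and a woman whose event would fall after the cut counts as event-free.

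Two things follow for this read-out. The overall MAAE percentage is too low for a 6-month endpoint. Any table by gestational age at vaccination (16-27 versus 28-38 weeks) also mixes a possible effect of timing with a difference in follow-up, so later vaccination tends to look safer. The second problem also reaches serious adverse events (SAEs) and adverse events of special interest (AESIs) when they are tabulated to Postpartum Day 43.

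**Working it through.** **Plan's own figures.** The SAP gives no follow-up or coverage figure for MAAEs. Its zero-event bounds in Section 3 reproduce (1 − 0.025^(1/N) gives 8.8%, 6.0%, 3.0% and 1.5% for N = 40, 60, 120, 240), but they do not bear on this point.

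**Inputs.** From the SAP: vaccination at Weeks 16 to 38 (taken as the week of enrolment), a cut 42 days after delivery, and a window of 6 months, taken as 183 days. Assumed, because the SAP does not give it: delivery at Week 40, with Weeks 37 to 42 as the range.

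**Follow-up at a per-woman cut.** Days observed = (delivery week − vaccination week) × 7 + 42. For delivery at Week 40:

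| Vaccinated at | Days observed | Share of 183 days |
|---|---|---|
| Week 16 | 24 × 7 + 42 = 210 | complete |
| Week 20 | 20 × 7 + 42 = 182 | 99.5% |
| Week 24 | 16 × 7 + 42 = 154 | 84% |
| Week 28 | 12 × 7 + 42 = 126 | 69% |
| Week 32 | 8 × 7 + 42 = 98 | 54% |
| Week 38 | 2 × 7 + 42 = 56 | 31% |

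**Break-even week.** Setting days observed to 183 gives vaccination week = delivery week + 6 − 183/7 = delivery week − 20.14. That is Week 19.9 for delivery at Week 40, 16.9 at Week 37 and 21.9 at Week 42. Even with delivery at Week 42, a woman vaccinated at Week 28 has 14 × 7 + 42 = 140 days. So over this range nobody vaccinated at Week 28 or later has a complete window.

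**Share incomplete.** Take delivery at Week 40 and vaccination uniform within each stratum. In the 16-27 week stratum, 1 − (19.86 − 16)/12 = 68% are incomplete; in the 28-38 week stratum, 100%. If 25% of women are in the later stratum, 0.75 × 68% + 25% = 76% are incomplete overall. If 75% are, 0.25 × 68% + 75% = 92%.

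**Mean window by stratum.** Assume vaccination uniform over Weeks 16 to 38 and mean delivery at Week 39.5.

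- Later stratum: the midpoint is Week 33, so the mean is 6.5 × 7 + 42 = 87.5, about 88 days.
- Earlier stratum: women vaccinated up to Week 19.36 are capped at 183 days. The rest fall linearly from 183 to 11.5 × 7 + 42 = 122.5 days, with mean 152.75. The stratum mean is (3.36 × 183 + 8.64 × 152.75)/12 = 161 days.
- Ratio: 161/88 = 1.8.
- Complete overall: 3.36/22 = 15%.

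A simulation with delivery at 39.5 ± 1.3 weeks gives the same 161 days, 88 days and 15%. For SAEs and AESIs to Postpartum Day 43 there is no 183-day cap. The earlier stratum then averages 17.5 × 7 + 42 = 164.5 days, a ratio of 164.5/87.5 = 1.9.

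**Illustration of the displayed percentage.** Assume the same true 6-month risk R in both strata and a constant hazard. The displayed risk is 1 − (1 − R)^(t/183). With R = 30%, t = 161 gives 27% and t = 88 gives 16%.

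**The case against.** **No data are lost.** This stands. The final analysis will hold the complete window, and 5.6.1.3 already requires tabulation over it. A reader might infer that the trial as a whole under-counts a primary endpoint. The SAP does not support that, because the shortfall belongs to the earlier read-out only.

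**The per-woman cut is not settled.** This stands in part. The trigger in 5.8.2 is a calendar event, and Table 3 uses a database cut-off date for interim analyses, including in phases that begin after Postpartum Day 42. Under one calendar date, women enrolled early could have complete windows, and the 15% figure would not apply. It would therefore be too strong to say that later data are certainly discarded for women who already have them. Against that, 5.8.2 limits the data by naming a visit, and Table 4 has the matching interval. Even a calendar cut leaves late-gestation women enrolled last incomplete.

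**A misleading table is not certain to appear.** This also stands in part. The content list in 5.8.2 is by example and does not name MAAEs, although it does not exclude them. Section 5.7.5 restricts subgroup tables to key safety analyses, and output detail is left to the Data Presentation Specifications. A table headed to Postpartum Day 43 would state its own window, but that heading would not equalise follow-up between subgroups.

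**The percentages rest on assumptions.** Correct. Enrolment pattern, delivery timing, risk level and constant hazard are not in the SAP. If MAAEs cluster soon after vaccination or around delivery, which are observed for every woman who stays to the cut, the gap shrinks. A reader should not take 27% versus 16% as a forecast.

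**The study is descriptive.** True, so no error rate is affected. But the descriptive incidence is itself the primary safety result.

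**Conclusion.** The point holds for the primary analysis, not for the trial's final reporting. With a per-woman cut, MAAE follow-up is incomplete for women vaccinated after about Week 20 (delivery assumed at Week 40; about Week 17 to 22 for delivery at Weeks 37 to 42) and for all vaccinated at Week 28 or later. With a single calendar cut-off fewer are affected, mainly those enrolled last.

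MAAE percentages at that read-out would be too low for a 6-month endpoint. Gestational-age comparisons of MAAEs, SAEs or AESIs would be confounded by follow-up that differs about 1.8- to 1.9-fold, given uniform enrolment and delivery near Week 39.5. The direction follows from the design; the size in percentage points is illustrative. Because 5.8.2 foresees regulatory use of these results and the correction is cheap, it should be made.

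**What to change.** - In 5.8.2, state whether the data cut is per participant or one calendar date.
- In 5.8.2 and 5.6.1.3, state that the 6-month MAAE endpoint is reported at the final analysis. At the primary analysis, label MAAE figures as data to postpartum Day 42.
- For gestational-age comparisons at the primary analysis, tabulate MAAEs, SAEs and AESIs either over a fixed post-vaccination window common to all women, such as 28 days, or as rates per person-time. Every woman who reaches the 42-day visit has at least 42 days of follow-up, so a 28-day window is complete for her.
- Count that window by date from vaccination, not by the Post-dose 1 period. Table 3 ends that period at birth, which is 2 × 7 = 14 days for vaccination at Week 38 and delivery at Week 40.

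The cost is a few sentences and one extra table from dates already recorded, with no change to trial conduct. The downside is that the full 6-month MAAE figure is available only at the final analysis.

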5.8.3. Final Analysis

The final analysis will be performed when all adult participants and all neonates/infants have completed the final visit per the Schedules of Activities.

6. SUPPORTING DOCUMENTATION

6.1. Appendix 1 List of Abbreviations

ADaM	Analysis Data Model
AE	adverse event
AESI	Adverse Event of Special Interest
ALT/SGPT	alanine aminotransferase
ASQ	Ages & Stages Questionnaire
ATC	anatomic and therapeutic class
BMI	body mass index
CD	cluster of differentiation
CDC	Center for Disease Control
CI	confidence interval
CI	total systemic clearance
CTP	Clinical trial protocol
CRF	case report form
CSP	Clinical Study Report
CTCAE	Common Terminology Criteria for Adverse Events
CV	coefficient of variation
	Deta Manitarina Committae
DMC	Data Monitoring Committee
DPS	Data Presentation Specifications
ELICA	electronic case report form
ELISA	enzyme-linked immunosorbent assay
ELISpot	enzyme-linked immunospot assay
FAS-A	Full Analysis Set-Adults
FAS-NVN	Full Analysis Set-Nonvaccinated Neonates
FDA	Food and Drug Administration
GMC	Geometric mean concentration
GMT	Geometric mean titer
ICH	International Conference on Harmonization
ICS	intracellular cytokine staining
IDMC	Interim Data Monitoring Committee
IFN-γ	interferon gamma
Ig	immunoglobulin
IL	interleukin
IQ	interquartile
LOD	limit of detection
LLOQ	lower limit of quantification
MAAE	Medically-attended adverse event
MedDRA	Medical Dictionary for Regulatory Activities
MIS-C	Multisystem Inflammatory Syndrome in Children
MRD	minimum required dilution
mRNA	messenger ribonucleic acid
MSD	Meso Scale Discovery
NAb	neutralizing antibodies
VNA	virus neutralization assav
PBMC	peripheral blood mononuclear cells
PD	pharmacodynamic(s)
PI	principal investigator
PK	nharmacokinetic(s)
PD	postpartum
	Per Protocol Immunogenicity Adulta
DDI NIVNI	Deer Drotogol Immunogenicity Negrotog
	Patient reported outcome
TKU «DT DCD	ration-reported outcome
YKI-PUK	quantitative Real-time polymerase chain reaction
KBD	receptor binding domain
KNA	ribonucieic acid

RT-PCR SAE	Real-time polymerase chain reaction serious adverse event
SARS-CoV-2	severe acute respiratory syndrome coronavirus-2
SAP	Statistical Analysis Plan
SD	standard deviation
SE	Standard Error
SIC	Symptoms of Infection
SMQs	standardised MedDRA queries
SDTM	Study Data Tabulation Model
TEAE	treatment-emergent adverse event
TH	T helper
TNFα	tumor necrosis factor alpha
TTS	Thrombocytopenia Syndrome
ULOQ	Upper limit of quantification
VNA	virus neutralization assay
WHO	World Health Organization
WHO-DD	World Health Organization Drug Dictionary

6.2. Appendix 2 Changes to Protocol-Planned Analyses

Not applicable.

6.3. Appendix 3 Demographics and Baseline Characteristics

Table 8 presents a list of the demographic variables that will be summarized by vaccination group and overall for the FAS-A analysis set. Demographics will also be summarized by country using the FAS-A analysis set.

Continuous Variables:	Summary Type
Age ([years])	
Weight (kg)	descriptive statistics (N, mean,
Height (cm)	and range [minimum and
Body Mass Index (BMI) (kg/m2) : (underweight <18.5 kg/m2; normal 18.5 - <25 kg/m2; overweight 25 - <30 kg/m2; and obese >=30 kg/m2)	maximum]
Categorical Variables:	
Age Group (18-34 years, 35-45 years)	
Gestational Age (16-27 weeks, 28-38 weeks)	
SARS-CoV-2 Serostatus at Baseline (Positive, Negative, Not evaluable,	
Missing)	
Race ^a (American Indian or Alaska Native, Asian, Black or African	
American, Native Hawaiian or other Pacific Islander, White, Not reported,	
Unknown)	Frequency distribution with the
Country (Country 1, Country 2,)	number and percentage of
Ethnicity (Hispanic or Latino, Not Hispanic or Latino, Not reported,	participants in each category.
Unknown)	
SARS-CoV-2 RNA Nasal Swab at Baseline (Positive, Negative, Missing)	
RT-PCR (Positive, Negative)	
Participant Educational Level	
Participant Living Status]
Participant Profession	

Table 8: Demographic Variables

^a If multiple race categories are indicated, the Race is recorded as 'Multiple'

